6.1.2 Hospital Sites

Participating hospitals must undertake a significant number (3000) of NCCT Head within the Emergency Department per annum. Specialty leads from radiology and Emergency Department will be identified with support from their NHS Trust/Board to participate in the deployment of qER. Hospitals that have already deployed qER or similar AI-enhanced NCCT head will be excluded. Sites were identified that provide good representation of potential heterogeneity (geographical, population, ethnicity, population age).

An independent statistician will perform a computerised randomisation of the clusters and keep randomisation records prior to the beginning of the data collection. Simple randomisation will be used to randomise one trust to receive the intervention in each of the

time periods. Local investigators will be notified ~6 weeks in advance of activation qER tool at their hospital.

6.2 Primary Outcome Measure

Time taken to report NCCT head from acquisition for patients with prioritised findings in Emergency Department compared to standard of care.

6.3 Secondary Outcome Measures

Utility of qER compared to standard of care:

- Time taken from acquisition to report NCCT head for patients without prioritised findings in Emergency Department
- Time taken from acquisition to report completed for patients with absence of findings on NCCT head scans in Emergency Department
- To assess impact of qER on radiology reporting workflow on other requests for CT scans
- To assess impact of teleradiology on qER supported reporting
- Time to diagnosis from CT acquisition.
- Time to referral from CT acquisition.
- Time to initiation of treatment from CT acquisition for prioritised scans.
- Death within 28 days of NCCT head acquisition
- Percentage of NCCT heads that qER classifies as prioritised and absence of findings.
- Percentage of qER non prioritised scans that radiologist identified as having prioritised finding
- Percentage of qER non prioritised but identified by radiologist as absence of finding.

Technical Evaluation of product performance:

- Sensitivity, specificity, positive and negative predictive values of qER in detecting scans with prioritized findings overall and also stratified by all 6 target abnormalities.
- Percentage of CT scans that could not be processed by qER due to technical factors.

Safety of qER:

- To assess the safety of qER of identifying patients with no prioritised findings identified on NCCT head.
- Percentage of patient NCCT Head reported incorrectly as qER non prioritised.
- Time from acquisition to reporting of CT Chest Abdo Pelvis (CAP) and Pulmonary Angiograms (CTPA) within the trust.

Health economic assessment:

- Compare costs and health benefits between pre and post implementation of qER, including cost evaluation of fully automatic diagnosis of high confidence normal triage.

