Figure 3: Example of current and proposed pathways for patients undergoing Head-NCCT scans from the Emergency Department.

“qER finding” workflow.

This will involve scans where qER identifies one or more of the target abnormalities which includes prioritised and non-prioritised findings. qER offers the opportunity to optimise NCCT finding detection. The study will integrate qER into ED clinical pathways (Figure 3). Images from ED pathway will be interpreted by qER and those identified to having the presence of any one or more of the prioritised findings will be flagged to radiologist for ‘prioritised’ reporting (allocated to duty radiologist). Along with the prioritised flag, radiologists can be provided with a secondary DICOM series with a contour that outlines the abnormality identified by qER. Following review, a radiology report will be generated and prioritised findings communicated to the ED clinician through existing escalation pathways. For scans where only non-prioritised finding have been detected by qER, they will also be flagged appropriately so that the reporting radiologist is informed of the same.

“No qER findings” workflow

qER also supports the workflow by ruling out target abnormalities. All images identified as absence of finding will be reviewed and reports verified.

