7 PARTICIPANT SELECTION

7.1 Study Population

At each of the four participating sites, we will identify all patients referred through the Emergency Department NCCT requests. Expected number of eligible participants and rationale behind sample sizing are detailed in the 'STATISTICAL CONSIDERATIONS' section.

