5.1. Summary

A data dictionary of a study explains exactly what data will be collected by each site and in what format. It explains the record type level (e.g., pre-scan, scan, post-scan, etc.) and attribute level (e.g., patient identifier, age, sex, date of referral, etc.) requirements. It can only be produced after an analysis of the data available at each site, to ensure study-wide consistency.

It will incorporate the following:

- Cohort and data selection criteria
- Source data format
- Data schema (record types along with their attributes, attribute formats, attribute capture requirement and attribute description)

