5.4 Schema

The following record types are to be extracted from routinely collected clinical data or data that is made readily available through the qER platform or from clinical fellow's report after he/she reviews the NHS trust radiology reports.

- Pre-scan
- Scan
- Post-scan
- Ground truth

Limitations of documented schema

- The list of attributes in each of the record types is not a comprehensive list. Additional attributes for study analysis may be **derived** from attributes listed below for each of the four record types during the study analysis phase of the study as applicable.
- The record types and attributes listed below are not the same as short datasets. A subset of attributes within each record type or a combination of attributes between multiple record types may constitute a short dataset depending on the feasibility of data capture. All record types will have one or more unique identifiers which can be used to merge multiple record types or multiple short datasets.

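### CT CAP/CTPA report time, the only defined measure of delay to non-head CT, is pooled across the trust and has no specified data source

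*Protocol*

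**What the plan says.** Under the safety heading, Protocol section 6.3 lists "Time from acquisition to reporting of CT Chest Abdo Pelvis (CAP) and Pulmonary Angiograms (CTPA) within the trust". It sets no limit by requesting location, worklist or time of day.

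The intervention is narrower. Section 6.1.1.3 says that ED head scans in which qER finds a prioritised abnormality "will be flagged to radiologist for ‘prioritised’ reporting (allocated to duty radiologist". The RIS order itself stays unchanged; the flag is what draws a scan forward.

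The data sections are written around head CT. In section 7.1, "we will identify all patients referred through the Emergency Department NCCT requests", and section 7.2 requires a head CT in the ED. Section 8.2 asks sites for pre-implementation volumes and intervals for head NCCT. Section 8.3 lists CT acquisition and report times without restricting them to head scans, but names neither CAP nor CTPA. Appendix 5 (5.1) says a data dictionary "explains exactly what data will be collected by each site and in what format". Its schema (5.4), introduced with "The following record types are to be extracted from routinely collected clinical data", has four record types: pre-scan, scan, post-scan and ground truth.

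**The concern.** If flagged head scans are read sooner by the same reader, something else on that reader's list may wait longer. For patients having a CT other than of the head, the CAP/CTPA outcome is where the plan would show this. Averaging it over the trust mixes scans that can be delayed with any that cannot, which pulls a real delay towards zero. For a safety measure that error is in the reassuring direction.

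The second problem is more basic. A before-and-after comparison needs acquisition and report times for CAP and CTPA scans in both phases, and no part of the protocol specifies that those rows will be extracted.

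**Working it through.** The protocol states no sample size, margin or power for this outcome, so there is no figure to reproduce. The check has three parts.

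1. Which outcomes in section 6.3 could show displacement?
   - "Time taken from acquisition to report NCCT head for patients without prioritised findings in Emergency Department": ED head scans only.
   - "Time taken from acquisition to report completed for patients with absence of findings on NCCT head scans in Emergency Department": ED head scans only.
   - "To assess impact of qER on radiology reporting workflow on other requests for CT scans": reaches beyond head CT, but defines no metric.
   - CAP/CTPA report time: beyond head CT, with a start point and an end point.

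   The 28-day mortality outcome is also confined to head NCCT patients. CAP/CTPA time is therefore the only defined metric for non-head CT.

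2. Where would the rows come from?

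| Place in Protocol | Covers | CAP/CTPA named? |
|---|---|---|
| 7.1, 7.2 | ED head CT | No |
| 8.2 | Baseline volume and intervals, head NCCT | No |
| 8.3, 13.1 | CT acquired and reported times, not limited to head | No |
| Appendix 5: pre-scan, scan, ground truth | Defined on head NCCT | No |
| Appendix 5: post-scan | Reported head findings and follow-up of the same scans | No |

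   No record type has a field for examination type or requesting location, so CAP and CTPA rows could not be told apart even if they were supplied in this format.

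3. How much would pooling dilute a delay? Let f be the share of trust CAP/CTPA scans on the same worklist as the flagged head scans, and d the relative delay in those scans. If both groups have the same average report time, the pooled delay is f × d. Assumptions, none given by the documents for this outcome: d = 20% (borrowed from the size of TAT change in section 15.1), SD equal to the mean, two-sided 0.05, 80% power, no clustering, f from 0.10 to 1.00.

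   Scans needed per period: n = 2 × (1.960 + 0.842)² / (f × d)². At f = 1 this is 2 × 7.849 / 0.04 = 392.4, rounded up to 393. The number rises as 1/f².

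   The last column holds the number of affected scans at 393 per period and adds the unaffected ones, so that n = 393/f and power = Φ(0.20 × √f × √(393/2) − 1.960).

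| f | Pooled delay | n per period for 80% power | Power with 393 affected scans |
|---|---|---|---|
| 1.00 | 20% | 393 | 80% |
| 0.75 | 15% | 698 | 68% |
| 0.50 | 10% | 1,570 | 51% |
| 0.25 | 5% | 6,280 | 29% |
| 0.10 | 2% | 39,245 | 14% |

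   Clustering by site would raise the absolute counts. The direction of the dilution does not depend on these assumptions; its size does.

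**The case against.** A reader might infer that CAP/CTPA time is the plan's only measure of harm to displaced patients. It is not. Unflagged ED head scans are the most obvious group to be overtaken, and two outcomes time them. On section 15.1's figures (35 × 4 × 12 = 1,680 abnormal scans; 1,680 / 0.10 = 16,800 in all) they number about 16,800 − 1,680 = 15,120, if abnormal is taken to mean prioritised. A third outcome names other CT requests, though without a metric.

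A reader might also infer that non-ED scans cannot be displaced. No section says what the duty radiologist's queue contains. If inpatient CAP or CTPA scans are read from it, the trust-wide measure captures them, and an ED-only outcome would leave out patients at risk. With f near 1 the dilution disappears.

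Finally, a reader might infer that the CAP/CTPA data will not be collected. The documents do not show that. Section 8.3 calls the dictionary an example. Appendix 5 says that its attribute list is incomplete and that the dictionary follows an analysis of each site's data. It mentions derived attributes, but does not say they are the only additions allowed.

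These points limit the claim without removing it. The scope of a secondary outcome could be refined in an analysis plan that is not shown, but an analysis plan cannot create rows that the data collection does not request. Nor does the open wording of section 8.3 supply a CAP/CTPA cohort when sections 7.1, 7.2 and 8.2 are all confined to head CT.

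**Conclusion.** The point stands in two parts. The missing data source is a mismatch within the protocol and needs no assumption: a listed safety outcome has no specified rows in either phase. The dilution is certain in direction for any f below 1 when the delay is confined to the shared worklist, but the documents give no means of sizing it. The 20% delay and the values of f above are illustrations only. That this outcome is meant to detect displacement is itself a reading, since section 6.3 does not state its purpose.

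The primary outcome is unaffected. The change is worth making before data extraction, because it is cheap then and pre-implementation rows may be harder to obtain later.

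**What to change.** In section 6.3, define the main analysis of this outcome on CT CAP and CTPA scans requested through the ED or read from the same worklist as the flagged head scans. Compare phases with the same site and calendar-month terms as the primary model in section 15.2. Keep the trust-wide figure as supportive.

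In Appendix 5, add a de-identified RIS record type holding site, examination code, requesting location or worklist, acquisition time, report time and in/out of hours, for the pre- and post-implementation periods. No clinical data are needed. Extend sections 7.1, 8.2 and 8.3 to cover these rows.

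The cost is one further export per batch, matching wording in the ethics and data-sharing documents, and fewer scans in the main analysis than a trust-wide count would give. Each site would also have to state which scans share the duty radiologist's worklist, which would supply the f that is now unknown.

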6.4 Technical Evaluation

The technical retrospective study will determine performance of the algorithm in each of the 4 sites. 500 NCCT scans will be identified for analysis from each site for technical evaluation. Sampling will be stratified by age, sex, month of year and target abnormalities.

The use of retrospective images and data has been approved by each site's Caldicott Guardian. In addition, approval for the release of anonymised patient data for research purposes forms part of the ethics application through IRAS.

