6.1.1.3 Post-Implementation

The implementation of new healthcare practices and the adoption of AI technologies is not linear. Study design and the elements of the study will enable evaluation of broadly the performance of the AI technology, acceptability, and the economic costs of adoption.

This randomised stepped wedge healthcare service delivery study to assess the clinical effectiveness of qER to prioritise patients reporting of NCCT scans that have prioritised findings (identified from AI analysis of a CT). The study will have an unaided (without qER

implemented) and aided phase (with qER implemented). During the unaided phase the reporting of CT will follow the same workflow as in the current standard of care (i.e., the images/cases will appear in the RIS chronologically and the radiologist either follows this order or prioritise some cases based on communication from ED). When the radiologist clicks a case in RIS, a secondary capture of qER along with the original images will be available in PACS.

During the post-implementation phase there will be a notification (prioritised flag) in RIS. The order of the cases in RIS will not be altered. When the radiologist clicks a case in RIS, a secondary capture of qER along with the original images will be available in PACS. This secondary capture will have contour showing the algorithm's attention point. The radiologist can choose to agree with qER findings as it or modify or ignore it according to their clinical judgement, writing and signing off the report. For scans which were not processed by qER the radiologist can prioritise and report as per the standard of care.

For the purposes of technical evaluation of qER, the scans taken during the aided phase will be divided into four categories:

- Scans with qER prioritised findings (prioritised pathway)
- Scans with qER non-prioritised findings (qER non-prioritised pathway)
- Scans not flagged as having no qER findings (qER no finding pathway), and
- Not interpreted (scans not processed by qER, Not interpreted pathway)

In the qER prioritised, qER non-prioritised and qER no finding pathway, all cases where the radiologist did not agree with qER findings will be sent for ground truthing (2+1 method, Figure 2). A random sample of 500 scans will also be sent for ground-truthing process for the purpose of technical evaluation.

[figure not shown]

Figure 2: Post-implementation workflow

[figure not shown]

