6.4.2 Outcome measures

- Sensitivity, specificity, positive and negative predictive values of qER in detecting scans with prioritized findings overall and also stratified by all 6 target abnormalities.
- AUC of qER in detecting presence of 6 target abnormalities

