6.5.3 Health Economic Data

The data elements that will be used for the analysis of health economic assessment are listed below:

Intervention and comparator

- Numbers of ground truth positive and ground negative cases
- AI false positives, true positives, false negatives, true negatives

- AI output (+/- per disease)
- Radiologist output and/or agreement with AI decision per scan
- Time of admission to ED
- Time (with and without qER) of CT scan
- Time (with and without qER) time to ER physician viewing scan
- Time (with and without qER) to radiologist open scan
- Time (with and without qER) to radiologist report / close scan
- Time (with and without qER) ER physician opens report
- Time (with and without qER) to onwards referral
- Time (with and without qER) to treatment (need specific treatment per speciality pathway e.g. time to embolisation, time to surgery etc)
- Time to AI output delivered to PACS

Resource Use

- Number of head CTs performed out of hours
- Number of head CTs performed in hours
- Definition of in and out of hours per trust
- Reason for the scan (primary suspected diagnosis and/or main symptom)
- Death
- Reattendance to hospital with same presentation
- Transfer to other hospital
- Admission to same hospital, including care pathway
- Clinical diagnosis, including sub-type and severity of (e.g ASPECTS score for stroke, any relevant head trauma scales)
- False negative outcomes (e.g. missed diagnoses and severity)
- False positive outcomes (e.g. misdiagnosis and severity)
- Length of stay and wait in the ED
- Length of stay in hospital / wait to transfer

Costs

- AI implementation, maintenance, training, per scan costs
- Treatment cost per pathway/speciality (to be sourced from published literature)
- ED visit cost (to be sourced from published literature)
- Cost of hospital admission (to be sourced from published literature)
- Cost of hospital transfer (to be sourced from published literature)
- Cost by ward type (to be sourced from published literature)
- Cost of outsourcing CT head reading in and out of hours (to be sourced from published literature)

Utilities

- Will be applied to patient outcomes (values to be sourced from published literature)

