The power estimations were conducted via a simulation approach. The range of conditions for sample size and intraclass correlation coefficient (ICC) were tested. The values of sample sizes tested ranged from 120 to 600 abnormal scans per site per year, while the range of ICC ranged from 0.05 to 0.30. Assuming type I statistical error at the $\alpha=0.05$ level and the total duration of the study 12 months the generalized linear mixed-effect regression model (GLMM) with expected distribution of the outcome variable Gamma the total sample size of 1,680 abnormal scans (35 abnormal per site/month; total yearly per site 420) ensures satisfactory level of statistical power exceeding 80% for detecting reduction in TAT by 20%. The models were estimated for abnormal cases. Assuming that abnormal cases are only ~10% of all CT scans performed at sites it can be expected that the total number of available scans in this study will be 16,800. Simulations were performed in R version v.4.1.0. If the study was conducted in a single hospital, this would not provide definitive evidence. However, if a similar impact is observed across four sites, especially if the time course of changes in multiple outcomes track the implementation of the intervention within each site, then the study will provide compelling evidence of the impact of the intervention. Given the expected amount of data that will be generated as part of the study, then it is expected that there will be good power to detect intervention effects within subgroups of patients, defined by age, sex, deprivation, and final diagnosis.

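### PPV and NPV are outcomes of a retrospective sample stratified on the abnormalities qER detects, with no allocation stated; unless allocation is proportional, the direct values describe the sampling mix

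*Protocol*

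**What the plan says.** Protocol section 6.4 (Technical Evaluation) sets the size of the retrospective sample: "500 NCCT scans will be identified for analysis from each site for technical evaluation". It then fixes how the scans are chosen: "Sampling will be stratified by age, sex, month of year and target abnormalities". The section gives no allocation across strata, no sampling fractions, and no statement of whether a scan's stratum comes from its clinical report or from another source.

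Section 6.4.2 lists the outcomes of this study: "Sensitivity, specificity, positive and negative predictive values of qER in detecting scans with prioritized findings overall and also stratified by all 6 target abnormalities", followed by the AUC for the six target abnormalities.

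The only prevalence figure is in section 15.1, in the power calculation for turnaround time: "Assuming that abnormal cases are only ~10% of all CT scans performed at sites".

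Two other places bear on the point. Section 6.3 lists the same accuracy measures as secondary outcomes. Section 6.1.1.3 adds a separate draw in the aided phase: "A random sample of 500 scans will also be sent for ground-truthing process for the purpose of technical evaluation".

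**The concern.** Stratifying on target abnormalities means selecting scans on the condition that qER is meant to detect. Sensitivity and specificity are conditional on true status, so they largely survive that kind of selection. PPV and NPV do not, because both depend on the share of abnormal scans in the sample. If that share is set by the sampling scheme, the direct ratios answer a question about the sample and not about patients in the ED.

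PPV tells a department how often a priority flag is a false alarm, and NPV tells it how far an unflagged scan can be trusted. Enrichment with abnormal scans would make the flag look more reliable than it is and an unflagged scan look less reliable than it is. Section 6.4 also aims to describe performance at each of the four sites, so different sampling mixes could look like differences in performance between sites.

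This belongs in the protocol because the protocol itself pairs this sampling scheme with these outcomes. A later analysis plan can weight the results only if stratum totals were kept when the scans were drawn.

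**Working it through.** **1. The plan's own figure.** Section 15.1 gives "35 abnormal per site/month; total yearly per site 420". 35 × 12 = 420 per site; 420 × 4 = 1,680 abnormal scans; 1,680 / 0.10 = 16,800 scans. Both totals agree with the protocol, so about 10% is the prevalence on which the plan rests. It refers to abnormal scans, which the protocol does not expressly equate with scans carrying a prioritised finding. Its use below is therefore an assumption.

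**2. Inputs not in the documents.** Sensitivity (Se) and specificity (Sp) are assumed to lie between 0.85 and 0.95. Sample shares of 25% and 50% abnormal are also assumed, as illustrations of enrichment.

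**3. Formulas**, with p the share of abnormal scans:

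- PPV = Se·p / [Se·p + (1 − Sp)(1 − p)]
- NPV = Sp(1 − p) / [Sp(1 − p) + (1 − Se)p]

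With Se = Sp = 0.90 and p = 0.10: PPV = 0.09 / (0.09 + 0.09) = 50.0%; NPV = 0.81 / (0.81 + 0.01) = 98.8%.
With p = 0.50: PPV = 0.45 / (0.45 + 0.05) = 90.0%; NPV is the same, 90.0%.

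**4. Over the assumed range** (PPV / NPV, %):

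| Share abnormal | Se = Sp = 0.85 | Se = Sp = 0.90 | Se = Sp = 0.95 |
|---|---|---|---|
| 10% | 38.6 / 98.1 | 50.0 / 98.8 | 67.9 / 99.4 |
| 25% | 65.4 / 94.4 | 75.0 / 96.4 | 86.4 / 98.3 |
| 50% | 85.0 / 85.0 | 90.0 / 90.0 | 95.0 / 95.0 |

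From the 10% row to the 50% row, PPV rises by 27.1 to 46.4 points and NPV falls by 4.4 to 13.1 points.

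**5. Weighting removes the shift.** Take 250 abnormal and 250 other scans with Se = Sp = 0.90: TP 225, FN 25, FP 25, TN 225. Weights back to 10% are 0.10/0.50 = 0.2 for abnormal scans and 0.90/0.50 = 1.8 for the others. Weighted PPV = 45 / (45 + 45) = 50.0%; weighted NPV = 405 / (405 + 5) = 98.8%.

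**6. Proportional allocation needs no weights.** With 50 abnormal and 450 other scans: TP 45, FN 5, FP 45, TN 405. PPV = 45/90 = 50.0%; NPV = 405/410 = 98.8%. The error is zero.

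**7. Is enrichment likely?** At 10%, a proportional draw yields 500 × 0.10 = 50 abnormal scans per site. The 95% half-width for Se = 0.90 is 1.96 × √(0.09/50) = 8.3 points, against 1.96 × √(0.09/250) = 3.7 points with 250. Estimates for single findings would be less precise still. This makes enrichment plausible but does not establish it.

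**The case against.** The strongest reply is that the protocol contains no wrong formula. Several stronger readings are tempting, and the document supports none of them.

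- **That the protocol prescribes an unweighted analysis.** It does not. Section 6.4 names strata and 6.4.2 names measures; neither fixes an estimator. Section 15.2 deals with turnaround time only. Weighting may be specified in a separate analysis plan, which was not available for this review.
- **That stratifying on abnormalities makes sense only with over-sampling.** Proportional stratification also has a purpose: it fixes the mix, guards against chance imbalance and reduces variance. Listing abnormality beside age, sex and month is consistent with that aim.
- **That strata might be formed from qER output, distorting sensitivity and specificity.** Nothing in section 6.4 says so.
- **That these counts feed the economic model.** Section 6.5.3 lists "AI false positives, true positives, false negatives, true negatives" as data elements but does not say that they come from this sample.
- **That safety conclusions would be too favourable.** Enrichment lowers NPV, so on that measure the error is conservative. Section 6.3 also has separate safety outcomes.

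A further reply is that the prospective phase can supply predictive values at natural prevalence, through the section 6.3 outcomes and the random 500 scans in 6.1.1.3. This stands in part. Under section 6.6, however, the original report becomes the reference standard wherever the radiologist agreed with qER, and that radiologist had qER's output available when reporting. The text of 6.6 requires independent reading only for disagreements and does not mention the random 500; its figures could not be read here. The prospective values therefore do not fully replace those planned in 6.4.2.

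**Conclusion.** The point holds as a conditional one. The protocol selects scans on the condition being detected and takes prevalence-dependent measures from the same sample, without stating the allocation that would make those measures interpretable.

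The possible error runs from zero under proportional allocation to a large one under enrichment. At an assumed 50% abnormal against an assumed 10%, and Se and Sp of 0.85 to 0.95, PPV is overstated by about 27 to 46 points and NPV understated by about 4 to 13. With Se = Sp = 0.90, a flag that is wrong half the time would appear wrong one time in ten. The same mechanism applies to predictive values for each single finding, whose prevalences the protocol does not give.

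The primary outcome is not affected. The point concerns listed outcomes of the technical evaluation and is worth settling before the scans are drawn.

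**What to change.** In section 6.4, state the allocation across strata and that strata are formed from the clinical report. Record each stratum's total and sampling fraction at each site. Then choose one of two routes.

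1. Weight every scan by the inverse of its sampling fraction when estimating sensitivity, specificity, PPV and NPV. This is the more complete route, because it also corrects for any disproportionate sampling by age, sex, month or type of finding.
2. Report only sensitivity, specificity and AUC from this sample, and compute PPV and NPV from them at each site's prevalence in consecutive ED scans.

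The cost is a few sentences of protocol text and the keeping of stratum totals, which are known when the sample is drawn. No extra scans or readings are needed. If allocation is proportional, one sentence saying so settles the matter: the weights are equal and no result changes.
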